## **3.0 OBJECTIVES**

### **3.1 Primary Objective and Hypothesis**

The primary objective is to compare the effectiveness of an intensive, 5-session, gender-specific group HIV/AIDS intervention for men, REMAS, to a standard single session HIV/AIDS education group. It is hypothesized that men provided REMAS will engage in fewer risky sexual behaviors as measured by the primary outcome measure of the number of unprotected vaginal and anal intercourse acts during the 90 days prior to the 3 and 6 month follow up assessments than will men provided the standard intervention. The time frame over which to measure risk behavior has varied from a few weeks to one year in studies examining sexual risk behavior. A shorter, more recent time frame should increase the reliability of the self report. A longer time frame provides greater opportunity for risk behavior to occur. This latter issue is especially important in populations such as drug abusers where frequency of sexual behavior varies greatly across and within individuals. The choice of a 90 day time frame provides a balance between these two issues. In addition 90 days was the time frame used in Project Light from which much of the intervention material is derived. It is also hypothesized that being non-monogamous in the prior six months and years of stimulant use will be associated with the frequency of unprotected vaginal and anal intercourse and intervention condition. Specifically, the intervention will be more effective with stimulant users and those with multiple sexual partners. These two variables will be entered into the data analytic model described more fully in section 11.2.

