where  $\varepsilon_k = (\varepsilon_{11k}, \dots, \varepsilon_{I(2m)k})'$  has a multivariate normal distribution with mean zero and covariance matrix  $\sigma^2 R$ . Here the correlation matrix  $R$  contains 1 for its diagonal entries and  $\rho$  for off-diagonal entries. Here  $\sigma^2$  is the variance of  $\varepsilon_{ijk}$  and  $\rho$  represents the correlation between any two observations from the same cohort as well as the correlation between two observations from different cohorts within the same CTP site. Note that we assume that the correlation between two observations from the same cohort is the same as the one between two observations from different cohorts within the same CTP site. Under this linear model, to detect the effect size  $\Delta$  in the average number of unprotected vaginal and anal intercourse between the intervention and control conditions at the type I error  $\alpha$  with a power of  $1-\beta$ , we need the following number of cohorts per condition in the study:

$$m = 2(z_{1-\alpha/2} + z_{1-\beta})^2 \{1 + (I-1) * \rho\} / (I * (\Delta)^2),$$

where  $z_{1-\beta}$  is the  $(1-\beta)$ th percentile of the standard normal distribution. This formula is the same as Formula (5.1) in Donner and Klar (2000).

From the above formula, we see that to calculate a required sample size we need to determine the standardized effect size  $\Delta$ . We have estimated the effect size on the basis of clinically important intervention effects observed in prior studies. The NIMH Multisite HIV Prevention Trial Group (1998) used the number of unprotected vaginal and anal intercourse acts as a primary outcome measure in Project Light. They observed an effect size ( $\Delta$ ) of 0.29. Assuming that we have an intracluster correlation no greater than  $\rho$  of 0.01 and an average of 8 participants per cohort ( $I=8$ ), using the above formula we find that the number of cohorts per condition required to detect the effect size of 0.29 with a type I error rate of 0.05 and a power of 80% is:

$$m = 2 * (1.96 + 0.84)^2 * \{1 + (8-1) * 0.01\} / (8 * (0.29)^2) = 25,$$

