To test this hypothesis, we let  $Y_{ijk}$  be the frequency of unprotected vaginal and anal intercourse of the  $i$ th subject in the  $j$ th cohort of the  $k$ th CTP site measured at the  $t^{\text{th}}$  follow-up time. Let  $z_{1ijk}$  be the treatment assignment indicator for the  $i$ th subject in the  $j$ th cohort of the  $k$ th CTP site. Here  $m$  is the number of cohorts per condition within the CTP site. To adjust for the possible imbalance between conditions on the baseline value, we include the baseline value as a covariate; let  $z_{2ijk}$  be the baseline frequency of unprotected vaginal and anal intercourse of the  $i$ th subject in the  $j$ th cohort of the  $k$ th CTP site. The other two covariates we plan to include in the model are (1)  $z_{3ijk}$ , a binary indicator on whether the  $i$ th subject in the  $j$ th cohort of the  $k$ th CTP site is non-monogamous in the six months prior to the baseline and (2)  $z_{4ijk}$ , years of stimulant use for the  $i$ th subject in the  $j$ th cohort of the  $k$ th CTP site. As noted by Sen (1997), analyzing change from baseline does not remove the baseline imbalance. Hence, we propose to model the absolute frequency at a particular follow-up time and include the baseline frequency value as a covariate in regression.

The following marginal model for outcome of count will be used to test this hypothesis:

$$(1) \quad \log E(Y_{ijk}) = \beta_0 + \beta_1 z_{1ijk} + \beta_2 t + \beta_3 z_{1ijk} * t + \gamma_1 z_{2ijk} + \gamma_2 z_{3ijk} + \gamma_3 z_{4ijk}$$

where  $t=0$  for 3 months post intervention and  $t=1$  for 6 months post-intervention.

Based on the assumed model (1), our main null and alternative hypotheses are governed by the regression parameters  $\beta_1$ ,  $\beta_2$  and  $\beta_3$ . For example,  $\beta_3 \neq 0$  indicates that over time the effects of the two study interventions are different;  $\beta_3=0$  corresponds to no difference in the effectiveness of the interventions over time. If  $\beta_3=0$ , the parameter  $\beta_2$  estimates the rate of change in the outcome measure from 3 to 6 months post-intervention in the two intervention groups, and the parameter  $\beta_1$  estimates the difference between the experimental and control intervention, which is the same at the two follow-up assessment times.

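### Section 11.6 enters the raw baseline count linearly under a log link, which forces an exponential baseline effect and gives up avoidable precision in the treatment estimate

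*Protocol*

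**What the plan says.** Protocol section 11.6 introduces model (1) with "The following marginal model for outcome of count will be used to test this hypothesis". The left side is log E(Y). The right side has treatment, time, their interaction, the baseline frequency of unprotected acts (z2, coefficient γ1), an indicator of non-monogamy and years of stimulant use. On z2 the text says "we propose to model the absolute frequency at a particular follow-up time and include the baseline frequency value as a covariate in regression". No log, cap, categories or spline is mentioned, and the equation shows a single term γ1·z2. The form is therefore stated, not left open for a later plan.

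The reason given for the term is balance: "To adjust for the possible imbalance between conditions on the baseline value, we include the baseline value as a covariate". Precision is not mentioned.

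On the spread of the data, section 3.1 remarks, when justifying the 90-day window in drug users, that "frequency of sexual behavior varies greatly across and within individuals". The protocol gives no mean, standard deviation, share of zeros or maximum for the count, and no correlation between baseline and follow-up.

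Section 11.7 applies the same models to the continuous-scale secondary outcomes, some of which are counts.

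**The concern.** Under model (1) each extra baseline act multiplies the expected follow-up count by exp(γ1). The step from 10 to 20 acts must have the same multiplicative effect as the step from 80 to 90. A simple relation, such as follow-up acts proportional to baseline acts, cannot be represented. A log baseline can represent it, approximately once a small constant is added.

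If the counts are right-skewed, as section 3.1 makes plausible, the few men with very high baseline counts largely set γ1. A slope fitted to them describes everyone else poorly. The residual variance that baseline adjustment should remove is then only partly removed, and the treatment coefficient β1 is noisier than it need be. β1 is also the quantity tested in the single futility analysis of section 11.9.

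**Working it through.** **1. Does the planned power depend on this term?** Section 11.3 sizes the trial "to detect the effect size of 0.29 with a type I error rate of 0.05 and a power of 80" percent, with "an average of 8 participants per cohort" and "Assuming that we have an intracluster correlation no greater than" 0.01:

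m = 2(1.96 + 0.84)² × {1 + (8 − 1) × 0.01} / (8 × 0.29²) = 2 × 7.84 × 1.07 / 0.6728 = 24.94, rounded up to 25 cohorts per condition.

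That is 8 × 25 = 200 per condition and 400 in all, as stated. The model behind the formula contains treatment only, so the stated 80% takes no credit for baseline adjustment.

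**2. What the functional form implies.** Suppose the truth is proportional: 20 baseline acts predict twice the follow-up of 10, and 90 acts predict 9 times.
- A slope matched to the low end is γ1 = ln 2 / 10 = 0.069. From 10 to 90 acts it predicts exp(80 × 0.069), about 256-fold instead of 9-fold.
- A slope matched to the whole range is γ1 = ln 9 / 80 = 0.027. From 10 to 20 acts it predicts exp(0.27), about 1.32-fold instead of 2-fold.

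**3. Leverage of high counts.** Assumed: 560 men, log-normal rates, baseline to follow-up correlation 0.5, raw count as covariate.

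| Log-SD | Leverage share of the top 5 men | Largest single leverage (mean) |
|---|---|---|
| 0.6 | about 15% | 0.20 |
| 1.0 | about 25% | 0.45 |
| 1.3 | about 30% | 0.56 |

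Five men are under 1% of 560.

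**4. Precision of β1, not assuming proportional rates.** Assumed: 560 men allocated 1:1, one follow-up time, no clustering or imputation, Poisson log-link fit with robust variance, 3,000 replicates. Variances are relative to no baseline adjustment. Share forfeited = 1 − (1 − raw)/(1 − log); for log-SD 1.0 this is 1 − 0.041/0.159 = 74%.

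| Assumed counts (correlation) | Raw | log(baseline + 1) | Gain forfeited by raw | Variance cut, log vs raw |
|---|---|---|---|---|
| Gamma, shape 2 (0.5) | 0.800 | 0.792 | 4% | 1% |
| Gamma, shape 1 (0.5) | 0.814 | 0.790 | 11% | 3% |
| Log-normal 0.6 (0.5) | 0.861 | 0.827 | 20% | 4% |
| Log-normal 1.3, capped at 180 (0.5) | 0.883 | 0.822 | 34% | 7% |
| Gamma, shape 0.5 (0.5) | 0.880 | 0.803 | 39% | 9% |
| Log-normal 0.8 (0.5) | 0.897 | 0.827 | 41% | 8% |
| Gamma, shape 0.5 (0.7) | 0.792 | 0.563 | 52% | 29% |
| Log-normal 1.0 (0.5) | 0.959 | 0.841 | 74% | 12% |
| Log-normal 1.3 (0.5) | 0.998 | 0.882 | 98% | 12% |

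The last column is 1 − log/raw. At an assumed log rate ratio of 0.3, power is 78% raw and 83% log for log-normal 1.0, and 43% and 48% for log-normal 1.3.

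**5. Precision of β1 when follow-up rates are proportional to baseline rates.** Assumed: 504 men (560 × 0.9) in 84 cohorts of 6, 18 settings, counts uncapped or capped at 180 or 90. The log form had lower variance than raw in every setting, by about 4 to 55%. Constants of 0.5 and 1 gave practically the same result. Raw was less precise than no adjustment only in the heaviest-tailed uncapped settings (gamma shape 0.5). In related runs without clustering, raw forfeited about 70% or more of the gain uncapped, 38–57% capped at 180 and 15–28% capped at 90.

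**6. Bias and imbalance.** In the uncapped settings of those runs (true rate ratio 0.7, log = −0.357), estimates averaged −0.345 to −0.364 under all three forms. The correlation between the arm difference in mean baseline count and the estimated β1 was 0.31 to 0.68 unadjusted, −0.05 to 0.06 with raw baseline and −0.14 to −0.01 with log baseline.

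**The case against.** The strongest defence is that the term does the job section 11.6 gives it. Step 6 shows that the raw count removes the average dependence of β1 on baseline imbalance, and the estimate is about unbiased. That stands. A reader might infer that a mis-scaled covariate corrects little imbalance or biases the comparison; neither the documents nor the checks support this.

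Second, the size of the loss depends on a tail that the protocol never quantifies. Section 3.1 supports a wide spread, but it speaks of sexual behaviour in general and gives no figure. Counts over 90 days may also have a practical ceiling, and capping shrinks the loss considerably. This stands too: that most of the gain is lost is one end of a range, not a fact about this trial.

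Third, the planned power takes no credit for the adjustment, and 560 men are planned against the 440 required with attrition. The point therefore cannot be read as showing that the trial is underpowered.

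Fourth, a log baseline is not free of choices. Eligibility looks back six months (section 5.4) and the baseline count 90 days (section 8.3.4), so zeros can occur. With a constant of 0.5, going from 0 to 1 act is a threefold step (1.5/0.5). This argues for fixing the details in advance. It does not rescue the raw form, which was never more precise than the log form in any setting run.

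**Conclusion.** The functional form is poorly chosen for a skewed count, and the protocol fixes it explicitly. The consequence is avoidable loss of precision in β1, from a small share of the adjustment gain with light-tailed or capped counts to all of it with heavy uncapped tails. A log baseline lowers the variance of β1 relative to raw by about 4 to 55% if follow-up rates are proportional to baseline rates, an assumption that favours the log form. Under the other structures tried the cut was 1 to 29%.

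All of this rests on assumed distributions and correlations. The simulations simplify the planned analysis, for example by leaving out imputation, and some also leave out clustering.

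A reader might also infer a false-positive problem. With the raw count, type I error in the 3,000-replicate runs was 0.049 to 0.066, apart from 0.075 in one heavy-tailed, high-correlation setting. That is too little to claim general inflation. The point is a cheap improvement, not a threat to validity.

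**What to change.** In section 11.6, define z2 as log(baseline count in the prior 90 days + 0.5). A constant of 1 would serve equally well; name one. Use the matching form wherever a baseline count enters a log-link model for a count secondary outcome in section 11.7. State now whether an indicator for a zero baseline count is included, so that no data-dependent choice is left in the primary model. Keep the raw-count version of model (1) as a named sensitivity analysis.

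The cost is the choice of a constant and one extra sensitivity analysis. No participants, visits or data items are added. The change should be made before any unblinded look, so that a few extreme baseline counts cannot later prompt a post hoc change to the primary model.

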### **11.3 Sample Size and Statistical Power**

The design of this study is a stratified cluster randomization trial (Donner & Klar, 2000). The randomization will be within strata (participating CTP site). A cluster is the cohort of 3-8 patients. Within each participating CTP site, cohorts of patients will be randomly assigned to the intervention or control conditions. Our sample size calculation is based on a comparison of outcomes between the intervention and control group measured at 6-month follow-up. This design has a two-level hierarchical structure, cohorts and CTP sites, resulting in two levels of correlation among subject’s responses: correlation due to cohorts and correlation due to CTP sites. Since the planned analyses will be based on the method of generalized estimating equation (GEE), our sample size calculation will be based on the formula given by

Liu and Liang (1997). Since we do not have any information on the relative magnitude of the possible correlation due to cohorts within CTP sites and due to CTP sites, we assume an equal correlation structure.

We let  $Y_{ijk}$  be the frequency of unprotected vaginal and anal intercourse of the  $i$ th subject in the  $j$ th cohort of the  $k$ th CTP site measured at the 6 month follow-up time, where  $i = 1, \dots, I$ ,  $j = 1, \dots, 2m$ , and  $k = 1, \dots, K$ . Let  $x_{ijk}$  be the treatment assignment indicator for the  $i$ th subject in the  $j$ th cohort of the  $k$ th CTP site. Here  $m$  is the number of cohorts per condition within the same CTP site.

We propose the following linear model for correlated data for our sample size calculation (Liu and Liang, 1997):

$$Y_{ijk} = \beta_0 + \beta_1 x_{ijk} + \varepsilon_{ijk},$$

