Therefore, we would require a total of  $8*25=200$  participants per condition, resulting in the total of 400 subjects in the study. Assuming each CTP site can contribute up to 40 subjects, the required number of CTP sites is 10. If each CTP site can only contribute an average of 32 subjects, we would require a total of 12 CTP sites. If each CPT can only contribute an average of 28, we would need a total of 14 CPT sites. Therefore, if we can recruit 14 good CTP sites, we would require each site to contribute a total of 28 subjects.

The following table provides estimates of the number of cohorts sites needed based on the above formula as should the average cohort size be less than 8.

I	# of the required cohorts per conditions
7	29
6	33
5	39
4	49

To allow a possible attrition rate of 10%, we would require a total of 440 participants for the estimate based on I=8. The investigators recognize that sample size calculations are best estimates based on previously obtained data when available. The effect size and intracluster correlation variation can result in significant variation in the sample sizes needed to obtain adequate power. For example if the intracluster correlation is twice what we are estimating (0.02) the total number of participants needed is 216 per condition or 476 total participants with 10% attrition rate. We propose to enroll 560 participants into the study. We feel this will provide some “cushion” for possible attrition, difficulty recruiting at any one site, or under estimation of the intracluster correlation.

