#### **11.6 Analysis of Primary Outcome**

The primary objective is to compare the effectiveness of REMAS, an intensive, 5 session, male-specific group HIV/AIDS intervention, to a standard single session HIV/AIDS education group. It is hypothesized that men provided REMAS will engage in fewer risky sexual behaviors as measured by the number of unprotected vaginal and anal intercourse acts than will men provided the standard intervention. It is also hypothesized that being non-monogamous in the prior six months, years of stimulant use, and the baseline frequency of unprotected vaginal and anal intercourse will be associated with the number of unprotected

vaginal and anal intercourse acts at follow up. These three covariates will be entered into the data analytic model described more fully below. All analyses will be performed using an ITT strategy consisting of all randomized participants. Since our data have two levels of the hierarchical structure, we will apply a marginal semi-parametric regression model to analyze the primary outcome.

Hypothesis 1: REMAS will significantly reduce the number of unprotected vaginal and anal intercourse at both at the 3 and 6 month follow-up times in comparison with the standard single HIV/AIDS education session.

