### 11.9 Interim Analyses

Given the absence of strong evidence supporting the impact of this intervention, as suggested by a reviewer we will plan to conduct an interim analysis, primarily for futility. We will use the method of stochastic curtailment using the conditional power method (Lan and Wittes, 1988; Jennison and Turnbull, 1999). This approach will provide the statistical rationale for consideration of early termination. We will briefly describe this interim analysis technique as follows.

Let  $T$  be the test statistics we will be using for testing the primary null hypothesis for our primary outcome  $H_0: \beta_1=0$  versus  $H_1: \beta_1 >0$ . We will perform one interim analysis when 50% of the participants have finished the 3 month follow up. Let  $D(1)$  denote the data accumulated when we perform the interim analysis. The formal stopping rule at the interim analysis is given as follows. We will first compute the conditional power, which is defined as follows:

$$P(0)=P(T \text{ will reject } H_0 \text{ at the end of the study} \mid D(1), \beta_1 =0).$$

Then, if  $1-P(0) \geq 0.8$  we will recommend to terminate the study early due to futility. If  $1-P(0) < 0.8$ , we will recommend the study be continued. For a detailed discussion of this approach, see Chapter 10 of Jennison and Turnbull (1999).

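### The only formal primary null, beta1 = 0, is the 3-month effect under model (1), but the trial is sized on 6 months and Hypothesis 1 claims both times; no test of either is written

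*Protocol*

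**What the plan says.** Four statements in the protocol bear on what the primary test is.

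- **Sizing (11.3).** "Our sample size calculation is based on a comparison of outcomes between the intervention and control group measured at 6-month follow-up". The cohort count for each arm "required to detect the effect size of 0.29 with a type I error rate of 0.05 and a power of 80% is" given as 25.
- **Hypothesis 1 (11.6).** "REMAS will significantly reduce the number of unprotected vaginal and anal intercourse at both at the 3 and 6 month follow-up times", compared with the single education session.
- **Model (1) (11.6).** The log mean count is beta0 + beta1·z1 + beta2·t + beta3·z1·t plus baseline covariates, where z1 is treatment, t = 0 is 3 months and t = 1 is 6 months. The text then says "our main null and alternative hypotheses are governed by the regression parameters" beta1, beta2 and beta3. It explains that if beta3 = 0, beta1 is a treatment difference common to both follow-ups. It does not say what is tested if beta3 is not 0.
- **Interim analysis (11.9).** The statistic T is described as the one for "testing the primary null hypothesis for our primary outcome", written as H0: beta1 = 0. The futility rule is the conditional power of T.

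**The concern.** The sections point at three different targets: 3 months (11.9 read with model (1)), 6 months (11.3) and both (Hypothesis 1). Section 11.6 should settle the matter. Instead it lists three parameters, one of which, beta2, is the control-arm change from 3 to 6 months and carries no information on efficacy.

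Two errors become possible. A real 6-month effect that is weak or absent at 3 months would probably be missed by the beta1 test, although 6 months is where the trial was powered. Conversely, an effect present at 3 months and gone by 6 months could be declared a success. The futility decision inherits the problem, because it too is built on beta1.

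**Working it through.** **1. What the coefficients mean.** Put the time codes into model (1) and take REMAS minus control on the log scale:

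- 3 months (t = 0): beta1
- 6 months (t = 1): beta1 + beta3
- control-arm change from 3 to 6 months: beta2

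So H0: beta1 = 0 is a statement about 3 months. It is also a statement about 6 months only when beta3 = 0.

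A simulation confirms this: 200 runs, 50 cohorts of 8, log-link GEE, no 3-month effect and a 6-month log rate ratio of -0.4. The mean count and its spread were assumed. The mean estimate of beta1 was -0.002, with rejection in 6.5% of runs. The mean of beta1 + beta3 was -0.399, with rejection in 97%.

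**2. Reproduce the sizing.** Inputs from 11.3: effect size 0.29, two-sided 5% (1.96), 80% power (0.84), and an intracluster correlation "of 0.01 and an average of 8 participants per cohort".

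m = 2 × (1.96 + 0.84)² × {1 + 7 × 0.01} / (8 × 0.29²) = 24.94, rounded up to 25. Then 25 × 8 = 200 per condition, "resulting in the total of 400 subjects in the study". This agrees with the protocol, as does its table for smaller cohorts (29, 33, 39, 49). On attrition the protocol says "To allow a possible attrition rate of 10%, we would require a total of 440 participants for the estimate based on I=8", which is 400 × 1.10. Planned enrolment is 560; less 10% that is 504, or 252 per arm.

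**3. Power of the beta1 test at 200 per arm.** I use the protocol's own standardised scale and assume the same standard error at each follow-up: SE = sqrt(2/200 × 1.07) = 0.1034. The expected z is the effect divided by SE, so 0.29 gives 2.80. The 6-month effect is held at 0.29 throughout.

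| 3-month effect | Power of beta1 test (two-sided 5%) |
|---|---|
| 0 | 5% |
| 0.10 | 16% |
| 0.145 | 29% |
| 0.20 | 49% |
| 0.29 | 80% |

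The 6-month value does not enter this calculation. The last row therefore also applies to an effect of 0.29 at 3 months that has vanished by 6 months. A test of beta1 + beta3 with a 6-month effect of 0.29 has 80.1% power at the same size.

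**4. Power if both times must be significant.** This is P(Z3 > 1.96 and Z6 > 1.96) for a bivariate normal with both means equal to 0.29/SE and correlation r. The protocol gives no 3-/6-month correlation, so r is an assumption.

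| r | 200 per arm | 252 per arm |
|---|---|---|
| 0.3 | 66.7% | 79.3% |
| 0.5 | 68.8% | 80.6% |
| 0.7 | 71.4% | 82.2% |
| 0.9 | 75.1% | 84.7% |

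**5. The average contrast, beta1 + beta3/2.** With 0.29 at both times, the expected z is 2.80/sqrt((1 + r)/2). Power at 200 per arm is then 93.5%, 89.9%, 86.0% and 82.0% for r = 0.3, 0.5, 0.7 and 0.9. With 0.29 at 3 months and 0 at 6 months, the expected z is 1.40/sqrt((1 + r)/2), and the test still succeeds 41%, 37%, 33% and 30% of the time.

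**The case against.** The strongest reply is that 11.6 does not put the primary test on beta1 alone. It names three parameters and says that beta1 is the common effect if beta3 = 0. In that case a beta1 test does bear on 6 months, with at least the planned power if the interaction is dropped. This stands: a reader might infer that the powered effect is never tested, and the protocol does not support so flat a statement. But the clause only interprets beta1 under a condition on an unknown parameter. Nothing says whether or when the interaction is dropped, or what is tested if beta3 is not 0.

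A second reply is that the exact contrast belongs in an analysis plan, and that estimates and variances for all coefficients are promised, so beta1 + beta3 can be derived. That would answer silence. Here the protocol does write a primary null, ties a stopping rule to it, and that null does not match its own sizing or hypothesis.

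A third reply concerns size, and it also stands. The 5% figure is the extreme case. The source trial is reported in 1.1.2 to have shown an effect at every follow-up. Enrolment of 560 also restores most of the power lost by requiring both times.

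A reader might further infer that the type I error is uncontrolled because a parameter could be picked after seeing the data. No such picking rule is written, and requiring significance at both times, as Hypothesis 1 reads, does not inflate the error.

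**Conclusion.** The inconsistency is real and should be corrected before the primary analysis and the futility look. As written, the one formal primary null is the 3-month effect under model (1). It reaches the 6-month effect on which the trial is sized only if beta3 = 0, and no test of beta1 + beta3 or of both times is stated.

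The cost depends on how the effect evolves. There is no loss against the planned 80% if the effect is 0.29 at both follow-ups. Power falls to 29% if the 3-month effect is half that size, and to 5% in the limiting case of none. Under the both-times reading the shortfall is material at 200 per arm and mostly gone at 252.

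These figures rest on the protocol's effect size, an intracluster correlation of 0.01, cohorts of 8, equal precision at the two follow-ups and, for the joint power, assumed correlations of 0.3 to 0.9. The standardised scale stands in for the log rate ratio, as it does in the protocol's own sizing.

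**What to change.** State one primary contrast in 11.6 and use the same one in 11.3 and 11.9.

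- **To match the sizing as written:** test beta1 + beta3 (6 months), two-sided at 5%, with beta1 and beta3 reported as supportive. N is unchanged. Hypothesis 1 should then be reworded to make 6 months the primary time.
- **If an effect at both times is the target:** require beta1 and beta1 + beta3 each to be significant at two-sided 5%, and restate the power in 11.3 with a stated 3-/6-month correlation.
- **In either case:** remove beta2 from the efficacy hypotheses, and rewrite the null and alternative in 11.9 for the chosen contrast.

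The average beta1 + beta3/2 is an option only if the sponsor restates both the hypothesis and the sizing. At present it matches neither, and it can succeed on an effect that has gone by 6 months.

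Model (1) and data collection stay as they are, so the cost is protocol wording, plus the power restatement in the second option. One consequence needs checking: the futility look is timed on 3-month completion, so the 6-month information available then should be set out when 11.9 is revised.
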